3.0 SCREENING AND STUDY ENROLLMENT PROCEDURES

Patient enrollment for this study will be facilitated using the Slot-Reservation System in conjunction with the Oncology Patient Enrollment Network (OPEN), a web-based registration system available on a 24/7 basis. It is integrated with the NCI Cancer Trials Support Unit (CTSU) Enterprise System for regulatory and roster data and, upon enrollment, initializes the patient position in the RAVE database.

Access requirements for OPEN:

Investigators and site staff will need to be registered with CTEP and have a valid and active Cancer Therapy Evaluation Program-Identity and Access Management (CTEP-IAM) account (check at <<https://ctepcore.nci.nih.gov/iam/index.jsp>>). This is the same account (user id and password) used for credentialing in the CTSU members' web site. To perform registrations in OPEN, the site user must have been assigned the 'Registrar' role on the relevant Group or CTSU roster. OPEN can be accessed at <https://open.ctsu.org> or from the OPEN tab on the CTSU members' side of the website at <https://www.ctsu.org>.

3.1 Current Study Status

Investigators should refer to the COG website to determine if the study is currently open for accrual. If the study is listed as active, investigators should then access the Studies Requiring Reservations page to ensure that a reservation for the study is available. To access the Studies Requiring Reservations page:

1. Log in to <https://open.ctsu.org/open/>
2. Click the **Slot Reservation** Tab. *The Site Patient page opens.*
3. Click the **Report** Tab. *The Slot Reservation Report opens. Available Slots are detailed per study strata.*

3.2 IRB Approval

NCI Pediatric CIRB approval or local IRB approval of this study must be obtained by a site prior to enrolling patients. Sites must submit CIRB/IRB approvals to the NCI's Cancer Trials Support Unit (CTSU) Regulatory Office and allow 3 business days for processing. The CTSU IRB Certification Form may be submitted in lieu of the signed IRB approval letter. All CTSU forms can be located on the CTSU web page (www.ctsu.org). Any other regulatory documents needed for access to the study enrollment screens will be listed for the study on the CTSU Member's Website under the Regulatory Tab.

Sites participating on the NCI CIRB initiative and accepting CIRB approval for the study are not required to submit separate IRB approval documentation to the CTSU Regulatory Office for initial, continuing or amendment review. This information will be provided to the CTSU Regulatory Office from the CIRB at the time the site's Signatory Institution accepts the CIRB approval. The Signatory site may be contacted by the CTSU Regulatory Office or asked to complete information verifying the participating institutions on the study.

Submitting Regulatory Documents:

Submit required forms and documents to the CTSU Regulatory Office via the Regulatory Submission Portal, where they will be entered and tracked in the CTSU RSS.

Regulatory Submission Portal: www.ctsu.org (members' area) → Regulatory Tab
→ Regulatory Submission

THIS PROTOCOL IS FOR RESEARCH PURPOSES ONLY, SEE PAGE 1 FOR USAGE POLICY

When applicable, original documents should be mailed to:

CTSUS Regulatory Office
[name]
[name]

Institutions with patients waiting that are unable to use the Portal should alert the CTSU Regulatory Office immediately at [name] in order to receive further instruction and support.

For general (non-regulatory) questions, call the CTSU General Helpdesk at [name] or contact CTSU by email at [contact].

Study centers can check the status of their registration packets by accessing the Site Registration Status page on the CTSU Member's Website under the Regulatory Tab. (Note: Sites will not receive formal notification of regulatory approval from the CTSU Regulatory Office.)

3.3 Patient Registration

Prior to enrollment on study, patients must be assigned a COG patient ID number. This number is obtained via the COG Registry in the OPEN system once authorization for the release of protected health information (PHI) has been obtained.

3.4 Reservation and Contact Requirements

Before enrolling a patient on study, a reservation must be made through the OPEN website and the Study Chair or Vice Chair should be notified. (The patient will need a COG patient ID number in order to obtain a reservation). Patients must be enrolled within 7 calendar days of making a reservation.

Reservations may be obtained 24-hours a day through the OPEN website.

3.5 Informed Consent/Assent

The investigational nature and objectives of the trial, the procedures and treatments involved and their attendant risks and discomforts, and potential alternative therapies will be carefully explained to the patient or the patient's parents or guardian if the patient is a child, and a signed informed consent and assent will be obtained according to institutional guidelines.

3.6 Screening Procedures

Diagnostic or laboratory studies performed exclusively to determine eligibility for this trial must only be done after obtaining written informed consent. This can be accomplished through one of the following mechanisms: a) the COG screening protocol, b) an IRB-approved institutional screening protocol or c) the study-specific protocol. Documentation of the informed consent for screening will be maintained in the patient's research chart. Studies or procedures that were performed for clinical indications (not exclusively to determine eligibility) may be used for baseline values even if the studies were done before informed consent was obtained.

3.7 Eligibility Checklist

Before the patient can be enrolled, the responsible institutional investigator must sign and date the completed eligibility checklist. A signed copy of the checklist will be uploaded into RAVE immediately following enrollment.

3.8 Institutional Pathology Report

Immediately following enrollment, the institutional pathology report for the diagnosis under which the patient is being enrolled must be uploaded into RAVE. The report must include the associated study number and COG patient registration and accession numbers. Personal identifiers, including the patient's name and initials must be removed from the institutional pathology report prior to submission.

3.9 Study Enrollment

Patients may be enrolled on the study once all eligibility requirements for the study have been met. Patients who give informed consent for the protocol in order to undergo screening for eligibility are not considered enrolled and should not be enrolled until the screening is completed and they are determined to meet all eligibility criteria. Study enrollment is accomplished by going to the CTSU OPEN (Oncology Patient Enrollment Network) <https://open.ctsu.org/open/>. For questions, please contact the COG Study Research Coordinator, or the CTSU OPEN helpdesk at <https://www.ctsu.org/CTSUContact.aspx>. Patients must be enrolled before treatment begins. The date protocol therapy is projected to start must be no later than five (5) calendar days after the date of study enrollment. **Patients must not receive any protocol therapy prior to enrollment.**

3.10 Dose Assignment

The dose level will be assigned via OPEN at the time of study enrollment.

4.0 PATIENT ELIGIBILITY

All clinical and laboratory studies to determine eligibility must be performed within 7 days prior to enrollment unless otherwise indicated. Laboratory values used to assess eligibility must be no older than seven (7) days at the start of therapy. Laboratory tests need **not** be repeated if therapy starts **within** seven (7) days of obtaining labs to assess eligibility. If a post-enrollment lab value is outside the limits of eligibility, or laboratory values are older than 7 days, then the following laboratory evaluations must be re-checked within 48 hours prior to initiating therapy: CBC with differential, bilirubin, ALT (SGPT) and serum creatinine. If the recheck is outside the limits of eligibility, the patient may not receive protocol therapy and will be considered off protocol therapy. Imaging studies, bone marrow biopsy and/or aspirate must be obtained within 14 days prior to start of protocol therapy (repeat the tumor imaging if necessary).

Clarification in timing when counting days: As an example, please note that if the patient's last day of prior therapy is September 1st, and the protocol requires waiting at least 7 days for that type of prior therapy, then that patient cannot be enrolled until September 8th.

Important note: The eligibility criteria listed below are interpreted literally and cannot be waived (per COG policy posted 5/11/01). All clinical and laboratory data required for determining eligibility of a patient enrolled on this trial must be available in the patient's medical or research record which will serve as the source document for verification at the time of audit.

4.1 Inclusion Criteria

4.1.1 Age:

- Part A: Patients must be ≥ 12 months and ≤ 21 years of age at the time of study enrollment.
- Part B: Patients must be ≥ 22 years and ≤ 30 years of age at the time of study enrollment until part A is complete. Part B will expand to include patients ≥ 12 months and ≤ 30 years of age once Part A is complete and once the initial 6 adult patients complete toxicity assessments per [Section 11.6](#).

4.1.2 Diagnosis:

- Part A: Patients with recurrent or refractory solid tumors are eligible, excluding CNS tumors. Patients must have had histologic verification of malignancy at original diagnosis or relapse.
- Part B: Patients with recurrent or refractory osteosarcoma are eligible. Patients must have had histologic verification of malignancy at original diagnosis or relapse.

4.1.3 Disease Status:

- Part A: Patients must have either measurable or evaluable disease (see Sections [12.2](#) and [12.3](#) for definitions).
- Part B: Patients must have measurable disease (see Section [12.2](#) for definition).

4.1.4 Therapeutic Options: Patient's current disease state must be one for which there is no known curative therapy or therapy proven to prolong survival with an acceptable quality of life.

4.1.5 Performance Level: Karnofsky $\geq 50\%$ for patients > 16 years of age and Lansky ≥ 50 for patients ≤ 16 years of age (See [Appendix I](#)). Patients who are unable to walk because of paralysis, but who are up in a wheelchair, will be considered ambulatory for the purpose of assessing the performance score.

4.1.6 Prior Therapy

4.1.6.1 Patients must have fully recovered from the acute toxic effects of all prior anti-cancer therapy and must meet the following minimum duration from prior anti-cancer directed therapy prior to enrollment. If after the required timeframe, the numerical eligibility criteria are met, e.g. blood count criteria, the patient is considered to have recovered adequately.

- a. Cytotoxic chemotherapy or other anti-cancer agents known to be myelosuppressive. See DVL homepage for commercial and Phase 1 investigational agent classifications. For agents not listed, the duration of this interval must be discussed with the study chair and the study-assigned Research Coordinator prior to enrollment.

≥ 21 days after the last dose of cytotoxic or myelosuppressive chemotherapy (42 days if prior nitrosourea).

THIS PROTOCOL IS FOR RESEARCH PURPOSES ONLY, SEE PAGE 1 FOR USAGE POLICY

- b. Anti-cancer agents not known to be myelosuppressive (e.g. not associated with reduced platelet or ANC counts): ≥ 7 days after the last dose of agent. See DVL homepage for commercial and Phase 1 investigational agent classifications. For agents not listed, the duration of this interval must be discussed with the study chair and the study-assigned Research Coordinator prior to enrollment.
- c. Antibodies: ≥ 21 days must have elapsed from infusion of last dose of antibody, and toxicity related to prior antibody therapy must be recovered to Grade ≤ 1 .
- d. Corticosteroids: See [Section 4.2.2](#). If used to modify **immune adverse events** related to prior therapy, ≥ 14 days must have elapsed since last dose of corticosteroid.
- e. Hematopoietic growth factors: ≥ 14 days after the last dose of a long-acting growth factor (e.g. pegfilgrastim) or 7 days for short-acting growth factor. For agents that have known adverse events occurring beyond 7 days after administration, this period must be extended beyond the time during which adverse events are known to occur. The duration of this interval must be discussed with the study chair and the study-assigned Research Coordinator.
- f. Interleukins, Interferons and Cytokines (other than Hematopoietic Growth Factors): ≥ 21 days after the completion of interleukins, interferon or cytokines (other than Hematopoietic Growth Factors)
- g. Stem cell Infusions (with or without TBI):
 - Allogeneic (non-autologous) bone marrow or stem cell transplant, or any stem cell infusion including DLI or boost infusion: ≥ 84 days after infusion and no evidence of GVHD.
 - Autologous stem cell infusion including boost infusion: ≥ 42 days.
- h. Cellular Therapy: ≥ 42 days after the completion of any type of cellular therapy (e.g. modified T cells, NK cells, dendritic cells, etc.)
- i. XRT/External Beam Irradiation including Protons: ≥ 14 days after local XRT; ≥ 150 days after TBI, craniospinal XRT or if radiation to $\geq 50\%$ of the pelvis; ≥ 42 days if other substantial BM radiation.
- j. Radiopharmaceutical therapy (e.g., radiolabeled antibody, ^{131}I -MIBG): ≥ 42 days after systemically administered radiopharmaceutical therapy.
- k. Patients must not have received prior exposure to VX15/2503

4.1.7 Organ Function Requirements

4.1.7.1 Adequate Bone Marrow Function Defined as:

- a. For patients with solid tumors without known bone marrow involvement:
 - Peripheral absolute neutrophil count (ANC) $\geq 1000/\text{mm}^3$
 - Platelet count $\geq 100,000/\text{mm}^3$ (transfusion independent, defined as not receiving platelet transfusions for at least 7 days prior to enrollment)
 - Hemoglobin ≥ 8.0 g/dL at baseline (may receive RBC transfusions)

- b. Patients with known bone marrow metastatic disease will be eligible for study provided they meet the blood counts in 4.1.7.1.a (may receive transfusions provided they are not known to be refractory to red cell or platelet transfusions). These patients will not be evaluable for hematologic toxicity. At least 5 of every cohort of 6 patients must be evaluable for hematologic toxicity for the dose-confirmation part of the study. If dose-limiting hematologic toxicity is observed, all subsequent patients enrolled must be evaluable for hematologic toxicity.

4.1.7.2 Adequate Renal Function Defined as:

- Creatinine clearance or radioisotope GFR $\geq 70\text{ml}/\text{min}/1.73 \text{ m}^2$ or
- A serum creatinine based on age/gender as follows:

Age	Maximum Serum Creatinine (mg/dL)	
	Male	Female
1 to < 2 years	0.6	0.6
2 to < 6 years	0.8	0.8
6 to < 10 years	1	1
10 to < 13 years	1.2	1.2
13 to < 16 years	1.5	1.4
≥ 16 years	1.7	1.4

The threshold creatinine values in this Table were derived from the Schwartz formula for estimating GFR (Schwartz et al. J. Peds, 106:522, 1985) utilizing child length and stature data published by the CDC.

4.1.7.3 Adequate Liver Function Defined as:

- Bilirubin (sum of conjugated + unconjugated) ≤ 1.5 x upper limit of normal (ULN) for age
- (ALT) (SPGT) ≤ 135 U/L. For the purpose of this study, the ULN for ALT is 45 U/L.
- Serum albumin ≥ 2 g/dL.

THIS PROTOCOL IS FOR RESEARCH PURPOSES ONLY, SEE PAGE 1 FOR USAGE POLICY

4.1.7.4 Adequate Pulmonary Function Defined as:

- a. No clinical indications such as evidence of dyspnea at rest, or exercise intolerance due to pulmonary insufficiency.
- b. If clinical indications, pulse oximetry >94% on room air.

4.1.8 **Informed Consent:** All patients and/or their parents or legally authorized representatives must sign a written informed consent. Assent, when appropriate, will be obtained according to institutional guidelines.

4.1.9 Tissue blocks or slides must be sent per [Section 8.7](#). If tissue blocks or slides are unavailable, the study chair must be notified prior to enrollment.

4.2 Exclusion Criteria

4.2.1 Pregnancy or Breast-Feeding

Pregnant or breast-feeding women will not be entered on this study. Pregnancy tests must be obtained in girls who are post-menarchal. Males or females of reproductive potential may not participate unless they have agreed to use two effective methods of birth control, including a medically accepted barrier or contraceptive method (e.g., male or female condom) for the duration of the study. Abstinence is an acceptable method of birth control.

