2.3.3 Pharmacology/Pharmacokinetics/Correlative and Biological Studies

The most accurate pharmacokinetic studies to date integrate the results of the Vaccinex phase 1 oncology and multiple sclerosis (MS) studies. Pharmacokinetic studies in adult oncology were limited due to inability to collect samples over a prolonged period of time. However, more extensive data collection points were obtained in the MS study allowing for more accurate assessment of T_{1/2} and AUC_{0-infinity}. Based on data collected from the MS study, the half-life appears to increase with dose (t_{1/2}, 20 days +/- 5 for 20 mg/kg dose, 15 days +/- 5 days for 10 mg/kg/dose) and clearance appears to decrease with dose (0.0201 L/hr +/- 0.0053 for 20 mg/kg dose). This may be explained by target-mediated drug disposition, which is commonly observed with monoclonal antibodies (MAbs).

Saturation of human T-cells with cSEMA4D was analyzed in the adult phase 1 study, with the threshold estimated to be approximately 0.3 microgram/mL. The extent of T lymphocyte associated SEMA4D saturation was dose independent, with weekly doses of VX15/2503 of 1 mg/kg or above producing complete, sustained cSEMA4D saturation. The time required for T-lymphocytes to become desaturated was dose dependent. Cellular SEMA4D desaturation occurred with VX15/2503 clearance from the periphery. The mean cSEMA4D saturation value at the end of infusion for all doses studied was 88% (range 68.5 to 98.7%). At the 1 mg/kg dose level, cSEMA4D saturation fell to approximately 20% at roughly 30 days post-infusion whereas full desaturation took greater than 155 days for the 20 mg/kg dose level. Cellular SEMA4D expression levels decreased approximately 50% following VX15/2503 binding to the cell surface receptor and its internalization, and returned to baseline expression levels with antibody clearance.^{11,14}

2.4 **Pediatric Studies**

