10.2 Off Study Criteria

THIS PROTOCOL IS FOR RESEARCH PURPOSES ONLY, SEE PAGE 1 FOR USAGE POLICY

- a) Thirty days after the last dose of the investigational agent.
- b) Death
- c) Lost to follow-up
- d) Withdrawal of consent for any required observations or data submission.
- e) Enrollment onto another COG therapeutic (anti-cancer) study
- f) The patient does not receive protocol treatment after study enrollment.

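### The contraception requirement normally lapses about 30 days after the last dose, when an estimated 35% of the drug level remains; state at least 6 months after the last dose in 4.2.1, 9.1.8 and 8.1 footnote 2

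*Combined protocol and SAP*

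**What the plan says.** Three places in the protocol set the contraception requirement, and they differ.

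- **4.2.1 (exclusion criteria):** two effective methods, "including a medically accepted barrier or contraceptive method (e.g., male or female condom) for the duration of the study". It applies to males and females of reproductive potential, and abstinence is accepted.
- **8.1, footnote 2:** one acceptable method for sexually active patients, also tied to the length of the study.
- **9.1.8 (Pregnancy & Lactation):** one effective method, during study therapy only.

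None states a period after the last dose. Section 10.2 lists when a patient goes off study. Item (a) is "Thirty days after the last dose of the investigational agent". Item (e), "Enrollment onto another COG therapeutic (anti-cancer) study", can come sooner.

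On persistence, 2.3.3 gives the adult half-life from the multiple sclerosis study as "20 days +/- 5 for 20 mg/kg dose". From the adult phase 1 oncology study it reports that "full desaturation took greater than 155 days for the 20 mg/kg dose level".

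On fetal risk, 9.1.8 says that no reproductive toxicology, genotoxicity or mutagenicity studies exist. Section 13.7.1 gives possible fetal exposure as the reason for expedited reporting of any pregnancy on study or within 6 months of the last dose.

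**The concern.** A patient who follows 4.2.1 to the letter could stop contraception about a month after the last infusion. A site that works from 9.1.8 could allow it at the last infusion. The half-life and the desaturation figure both suggest that a good deal of antibody is still present then. After day 30 the patient is normally off study, and the pregnancy tests in 8.1 are tied to disease evaluations, so no further test is scheduled.

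The stake is an avoidable, unstudied fetal exposure. The population makes this relevant: Part B enrolls up to age 30 and opened first to ages 22 to 30. The trial's own sampling will not settle when the effect ends. The saturation samples in 8.5.2 normally fall no later than about two weeks after a dose (Cycle 1 Day 28 is 13 days after the Day 15 infusion), and none is planned later in the decline.

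**Working it through.** **Inputs**

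- Dose and interval: 20 mg/kg every 14 days (2.5, 5.4).
- Half-life T at 20 mg/kg: 20 days, with 15 and 25 as the range (2.3.3).
- Off study: day 30 after the last dose (10.2a).
- Desaturation at 20 mg/kg: more than 155 days (2.3.3).
- Pregnancy reporting window: 6 months, taken as 182 days (13.7.1).

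First-order decline is assumed.

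**The plan's own half-life arithmetic.** The plan states no residual at 30 days. The nearest figure is in the dose rationale (2.5): steady state in 5 to 6 doses, based on the 15-day half-life at 10 mg/kg. The fraction of steady state after n doses is 1 − 2^(−14n/T). With T = 15:

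- n = 5: 1 − 2^(−70/15) = 96.1%
- n = 6: 1 − 2^(−84/15) = 97.9%

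The plan's statement reproduces, so the same model is used below.

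**Level remaining after the last dose.** The fraction is 2^(−t/T). Accumulation at steady state is 1/(1 − 2^(−14/T)).

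| | T = 15 d | T = 20 d | T = 25 d |
|---|---|---|---|
| Remaining at day 30 | 25.0% | 35.4% | 43.5% |
| Accumulation, dosing every 14 days | 2.10 | 2.60 | 3.11 |
| Day-30 level at steady state, relative to the peak after one dose | 0.53 | 0.92 | 1.35 |
| Five half-lives | 75 d | 100 d | 125 d |
| Remaining at day 182 | 0.02% | 0.18% | 0.64% |

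For T = 20, the day-30 entry is 2^(−30/20) = 2^(−1.5) = 0.354. The third row is the product of the first two, for example 0.354 × 2.60 = 0.92. In a patient treated to steady state, the level at day 30 is therefore close to the level just after a first infusion.

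**Candidate periods compared.** Thirty days is 1.5 half-lives (1.2 to 2.0). Six months is 182/20 = 9.1 half-lives (7.3 to 12.1). It exceeds five half-lives across the range, passes the 155-day figure by 27 days and equals the window in 13.7.1.

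**The case against.** **The 30-day end is inferred.** Section 4.2.1 does not cite 10.2. It is the natural reading, but the defect could also be described as an undefined term. Either way, a stated period is missing.

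**The consent form may say more.** Consent pages were not available, and post-treatment instructions to patients could be there. That would reduce the practical risk. It would not reconcile the three protocol wordings.

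**A reporting window can rightly be wider than a contraception period.** This stands. A reader might infer that 13.7.1 contradicts 4.2.1, but the two can coexist. Section 13.7.1 shows only that the protocol regards exposure up to 6 months as worth tracking.

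**Six months is not derived from a desaturation limit.** This also stands. Five half-lives alone would support 75 to 125 days, and the 155 days is a lower bound whose starting point is not stated.

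Two stronger readings are tempting, and the documents do not support them.

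- *Full saturation at day 30.* A reader might note that 35% of 20 mg/kg is about 7 mg/kg and pair it with the statement in 2.3.3, "with weekly doses of VX15/2503 of 1 mg/kg or above producing complete, sustained cSEMA4D saturation". That result concerns repeated weekly doses, not a one-time residual. The same section reports that saturation at the 1 mg/kg level fell to about 20% at roughly 30 days after infusion. Saturation at day 30 after a last 20 mg/kg dose is not reported.
- *A modelled desaturation date beyond six months.* A reader might combine the half-life, the clearance ("0.0201 L/hr +/- 0.0053 for 20 mg/kg dose") and the saturation level ("with the threshold estimated to be approximately 0.3 microgram/mL"), assume 70 kg, and extrapolate to a time. Those inputs fail against the 1 mg/kg result. The volume is 0.0201 × 24 × 20 / ln 2 = 13.9 L. A 70 mg dose then gives 5.0 microgram/mL, and 5.0 × 0.354 = 1.8 microgram/mL at day 30. That is six times the threshold, at a time when only about 20% saturation was seen. Section 2.3.3 also reports a shorter half-life at 10 mg/kg than at 20 mg/kg and suggests target-mediated disposition, so a fixed 20-day half-life should not be carried down to the threshold.

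**Conclusion.** The point holds as a low-cost improvement that should be made. As written, contraception may normally stop 30 days after the last dose, or at the last infusion under 9.1.8. About 35% of the post-dose level (25% to 44%) then remains at day 30, and full desaturation at this dose took more than 155 days.

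The percentage assumes first-order decline at an adult half-life from another disease. No pediatric half-life is given, and target-mediated clearance may speed the late decline. The reported desaturation time supports long persistence without relying on that model.

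A reader might also infer that fetal harm is shown. It is not. Section 2.2.2 describes functional immune defects in mice lacking SEMA4D, but no apparent abnormality in other tissues and no bony malformations. The toxicology studies reported a no-adverse-effect level of 100 to 200 mg/kg. With no reproductive toxicology, these data justify caution and no more.

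The number of people affected cannot be given. Section 11.4 plans 71 patients (30 female, 41 male) and 11.1 allows up to 75. Neither says how many are of reproductive potential, and eligibility starts at 12 months of age.

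**What to change.** In 4.2.1, 9.1.8 and footnote 2 of 8.1, require contraception *during study therapy and for at least 6 months after the last dose of VX15/2503, regardless of off-study status*. Align the number of methods with 4.2.1, keeping abstinence as accepted. Two methods are already a condition of entry there, so this adds no new duty. The sponsor may set a separate, justified period for males, because 13.7.1 concerns patients who become pregnant.

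Match the consent form if it does not already say this. Changing an eligibility criterion does not by itself bind patients already enrolled, so notify those on therapy and those within 6 months of their last dose, where they can be reached. Some who withdrew consent or moved to another study may not be reachable.

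Give the reason in the text: six months exceeds five half-lives (75 to 125 days) and the 155-day lower bound, and matches 13.7.1. Do not present it as a proven limit for desaturation.

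Cost: a wording amendment at three places, a consent line if needed, one notice, and about five more months of contraception for patients of reproductive potential. It adds no visits, samples or patients.
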